Appendix D – Survey used to measure intervention acceptability, appropriateness, and feasibility
Acceptability of Intervention Measure (AIM)

For the statements below, please circle or place a check by all the choices which apply to you

- 1) Phexxi meets my approval.
- 2) Using Phexxi is appealing to me.
- 3) I like using Phexxi.
- 4) I welcome Phexxi as a way to prevent my recurrent BV/yeast infections.

Intervention Appropriateness Measure (IAM)

- 1) Phexxi seems fitting to use as a prevention tool against BV and yeast infections.
- 2) Phexxi seems suitable to use as a prevention tool against BV and yeast infections.
- 3) Phexxi seems applicable to use as a prevention tool against BV and yeast infections.
- 4) Phexxi seems like a good match to use as a prevention tool against BV and yeast infections.

Feasibility of Intervention Measure (FIM)

- 1) Using Phexxi seems implementable.
- 2) Using Phexxi seems possible.
- 3) Using Phexxi seems doable.
- 4) Phexxi seems easy to use

In the space below, please share any additional comments you have about your experience using Phexxi

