Title: Exploring the effects of an intravaginal lactic acid gel on the vaginal microbiome

Version Date: November 23, 2022

Principal Investigator: [name] MPH

Co-Investigator(s): [name], DO, [name] MPH

Research associates: [name], [name] and [name] (SRI)

Research Site(s): The Queen's Medical Center, [name]

Abbreviations:

- **BV: bacterial vaginosis**
- **CV: candida vaginitis**
- **HRT: hormone replacement therapy**
- **CST: community state types**

Section I: Purpose and Background

1. Specific aims and objectives:

This project aims to investigate if the contraceptive method, Phexxi, causes changes to the composition of the vaginal microbiome. We hypothesize that regular use of Phexxi will cause increased colonization of lactic acid-producing lactobacilli, which could have positive effects in the way of preventing recurrent episodes of BV and candida infections.

Primary outcomes

- To assess if the use of Phexxi causes changes in the vaginal microbiome
- To assess if the use of Phexxi decreases vulvovaginitis symptoms in study participants

Secondary outcome

- To assess patient satisfaction/acceptability of this intervention as a therapeutic/prophylactic agent for recurrent vulvovaginitis

2. Background, significance, and rationale

Bacterial vaginosis (BV) and candida vaginitis (vaginal yeast infection) are debilitating, long-term conditions which have been associated with decreased confidence and self-esteem, difficulty with sexual intimacy, and decreased quality of life amongst women who suffer from one or both chronically. BV has a particularly high rate of recurrence, with an estimated 30% of infections recurring within three months of treatment, and an estimated 50% of infections recurring within six months of initial treatment¹.

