Once received at the research site, samples will be stored in a specimen freezer at -80 degrees F until all specimens are received, at which point they will analyzed using NextGen sequencing, a DNA sequencing technology that will identify the genetic makeup of their specimens. This will be done to sequence the genome of the bacteria of the microbiome, not the patient's genetic material. The first phase of the study will also include a survey (Appendix B), which will collect demographic information from each participant, as well as assess patients' current acceptability of a vaginal gel for prophylactic use, their most bothersome symptoms, and how their quality of life is affected by recurrent vulvovaginitis. The specific information collected from each

participant can be found below in Data Analysis. The survey used to measure this will be the **Vulvovaginal Symptom Questionnaire (VSQ)**, which has been validated for the purposes stated above (Appendix C). There will also be an added space in the survey provided for open-ended answers and comments.

Measurement for primary outcomes will be done using two separate methods. In order to assess for the presence of lactic acid-forming organisms before and after the lactic acid gel intervention, NextGen DNA sequencing will be completed on self-collected samples submitted by participants. The analysis of these samples will be performed by [name], at an in-house lab run by the UH Maternal Fetal Medicine division. In order to assess for patient-experienced symptoms, **survey B (Appendix C) will be administered prior to, immediately after, and 30 days after intervention.**

In order to measure our secondary outcome, Survey C (Appendix D) will be administered at collection points 2 and 3.

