Survey B, completed at the first, second and third collection time points will assess the symptom profile of each patient. Survey B is modified version of the VSQ (vulvovaginitis symptom questionnaire, which is a validated tool used to assess vulvovaginitis symptoms. A blank space will also be provided to allow for free text answers. These answers will be assessed qualitatively, looking for key themes within the answers provided.

To assess for the secondary outcome, Survey C, delivered at the second and third time point, will ask the patient what their satisfaction and acceptability ratings for Phexxi use as a prophylactic agent for vulvovaginitis are. Survey C is a validated tool, used to measure the acceptability, appropriateness, and feasibility of an intervention. A blank space will also be provided to allow for free text answers. These answers will be assessed qualitatively, looking for key themes within the answers provided.

3. Data storage, security, and confidentiality:

Patient information will be de-identified and connected to a unique Study ID. All identifiable information will be stored in a password protected and encrypted computer in the PI's research office at QMC, which is secured at the 1004 clinic. The signed consent forms will also be stored at the 1004 clinic, in a folder located in a locked office. Only the PI and [name] will have access to the identifiable information. [name], who will be performing analysis using specimens pre-labeled with the study ID, will not have access to participant PHI.

If participants opt, in their initial consent, to receive a copy of their vaginal microbiome results, the results will be sent to them via email, using a QMC email address. In order to encrypt this email, the function [encrypted] will be placed in the subject line.

4. Transition from research participation (if applicable): – Not applicable

5. Study timeline:

As the participation of subjects is not directly reliant on one another, data collection will begin as soon as the first subject is enrolled, and will continue until 30 days after the last subject completes the intervention. We hope for the total timeline to be approximately 1 year, which allow for time for data analysis and write-up of the intervention results.

Section IV: Risk/Benefit Assessment

1. Risk category (Minimal or Greater than Minimal): This study poses minimal risk to the patient.

2. Potential risk(s):

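### Survey C is meant to give acceptability ratings, but the form as shown is a tick-all list on which a blank has no single meaning; the baseline acceptability measure is on neither baseline form

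*Protocol*

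**What the plan says.** Section I.1 of the protocol names one secondary outcome: "To assess patient satisfaction/acceptability of this intervention as a therapeutic/prophylactic agent for recurrent vulvovaginitis". Section III.1 gives the timing: "Survey C (Appendix D) will be administered at collection points 2 and 3". Section III.2 describes what the form delivers. It "will ask the patient what their satisfaction and acceptability ratings for Phexxi use as a prophylactic agent for vulvovaginitis are", and "Survey C is a validated tool, used to measure the acceptability, appropriateness, and feasibility of an intervention". Section III.2 adds that free-text answers on the form will be read qualitatively for themes.

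The form itself is Appendix D. It lists four statements under each of three headings (acceptability, appropriateness, feasibility). Its only response instruction, printed once under the first heading, is "For the statements below, please circle or place a check by all the choices which apply to you". It ends with a space for comments.

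On the baseline, Section III.1 says that the first-phase survey (Appendix B) will collect demographics and also "assess patients' current acceptability of a vaginal gel for prophylactic use", along with bothersome symptoms and quality of life. It then names the VSQ (Appendix C) as the validated instrument for these purposes.

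**The concern.** A rating needs a graded answer to each statement. A tick-all list gives one positive response and an absence. Because all 12 statements are favourable, that absence has to stand for disagreement, indifference and non-response together. If the form is used as shown, the sole secondary outcome cannot be reported as the ratings that Section III.2 describes. No later scoring rule or analysis can separate answers that the form did not separate. The statement that the tool is validated would also need qualifying if its response format has been changed.

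The ambiguity has practical weight here. Section III.1 has participants take the surveys home in the study kit and answer the third set through an emailed link, so no staff member is present to notice a skipped statement. Dislike is also a realistic answer: Appendix F lists burning in 18.0% and pruritus in 14.5% of users in the product's contraceptive studies.

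The baseline point is a mismatch between text and form: the protocol says something is measured that neither baseline form asks about.

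**Working it through.** No figure stated in the protocol is at issue, so there is none to reproduce. The check sets the text beside the forms and counts.

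**Survey C (Section III.2 against Appendix D)**

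- Statements: 3 subscales × 4 = 12, all favourable.
- Answers per statement as shown: tick or blank. No anchors, no disagree option and no box for none of these.
- Most that can be derived per subscale: a count of ticks from 0 to 4; overall, 0 to 12. This count is my construction, since the protocol gives no scoring rule.
- Readings of a blank: at least three (disagree, neutral, skipped). A participant who rejects all four statements of a subscale and one who overlooks that block both produce 0.
- Reach: 12 statements × 2 administrations = 24 responses per participant.

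The instruction is printed once, under the first heading. If it covers all three blocks, which is the natural reading, all 12 statements are tick-all. If it covers only the first, the other 8 have no response instruction. Neither reading yields a rating.

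**Possible size of the ambiguity**

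Section II.1 plans for 20 participants after allowing for drop-outs from 22 enrolled. Suppose the result for a statement is the proportion ticking it, with 20 as denominator. A participant who would have ticked it but skipped it lowers that proportion by 1/20 = 5 percentage points; two such participants lower it by 2/20 = 10 points. One or two skips is an assumption chosen for illustration, as the protocol gives no expected rate of item non-response.

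**Baseline acceptability (Section III.1 against Appendices B and C)**

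| Form | Content | Items on acceptability of a gel |
|---|---|---|
| Appendix B | 8 items: age, race, ethnicity, infections, birth control, diet, conditions, medications | 0 of 8 |
| Appendix C | 21 items on symptoms, their impact and sexual activity | 0 of 21 |
| Appendix D | 12 statements about Phexxi | not given at baseline |

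The "current acceptability of a vaginal gel for prophylactic use" that Section III.1 promises therefore has no item on a form completed before treatment.

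**The case against.** **A response grid may have been lost.** The text was read from a PDF and tables can break. The word for choices in the instruction could refer to answer options that did not survive, and the version behind the emailed link may be laid out differently. The caveat stands, so the absence of a scale is stated here only of the form as shown. It is unlikely to be the explanation, because an invitation to mark everything that applies does not fit a grid with one answer per row. That the 0/1 codes of Appendix C survived is weak evidence, since they are inline text. If a grid does exist, the instruction still conflicts with it.

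**Unfavourable views can be recorded.** This is correct. A reader might infer from 12 favourable statements that a participant has no means of expressing dislike. Appendix D has a comment box, Section III.2 commits to analysing it for themes, and the Appendix E diary takes side effects. The gap is narrower: the 12 items carry no unfavourable response, and free text supplies no rating.

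**No rule treats blanks as disagreement.** Also correct. A reader might infer that missing answers will be scored as disagreement. The protocol states no such rule, and scoring and missing-data rules may sit in an analysis plan that is not at hand. Such a plan could choose a convention for blanks, but it could not find out what each blank meant.

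**No change-from-baseline analysis is lost.** Correct again. A reader might infer that a before-and-after comparison of acceptability has been made impossible. None is planned: the secondary outcome concerns the intervention itself and is measured at collections 2 and 3 only. The baseline wording concerns vaginal gels in general, while Appendix D asks about Phexxi, partly from experience of using it.

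**Conclusion.** The point holds in two parts of unequal weight.

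The main part is that the text promises ratings from a validated tool and the form as shown collects ticks. It affects every statement of the only measure of the only secondary outcome, at both administrations. It rests on two assumptions: that no response grid was lost in reading the PDF, and that the single instruction governs all three subscales. The second matters little, since without it 8 statements have no instruction at all. The shift of 5 to 10 percentage points in a proportion is an illustration for one or two skips among 20, not an estimate.

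The lesser part is that the stated baseline measure of acceptability appears on neither baseline form. This does not depend on the layout of Appendix D, and no stated endpoint is lost by it.

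This is an uncontrolled pilot, and neither part touches the primary outcomes or the sample size. The main change is still worth making before the forms are used, because what the form does not collect cannot be recovered afterwards.

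**What to change.** 1. In Appendix D, replace the tick-all instruction with one required graded answer per statement, for example five levels from completely disagree to completely agree, and state that it applies to all three subscales. On the linked electronic survey the answer can be made mandatory. On paper, ask for one mark per row and check the form when it is returned. If the actual form already has a grid, only the instruction needs correcting.
2. If the tick-all format is kept on purpose, remove the reference to ratings in Section III.2, define the result as a count or proportion of statements ticked, and qualify the claim of validation.
3. Either add a short baseline item on acceptability of a vaginal gel, using the same scale, or delete that statement from Section III.1.

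The cost is one reformatted form, at most a few added questions, and about a minute more per participant. Deleting the baseline statement costs nothing in data collection.

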Appendix E Patient symptom diary

Subject ID

DATE	TIME		Was the product used today?	Side effects or symptoms experienced	Other events (example: menstruation, intercourse, new medications)

Please return this diary with your second collection specimen, 30 days after you have completed the study drug.

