After obtaining informed consent, the research team will review standardized instructions for using the study medication with the patient and the research associate will provide a take-home kit including all of the study materials, including instructions for collecting each swab (Appendix A) and for returning the samples. Samples will be self-collected by participants at their home at intervals specified in the study instructions. All materials provided to the patient will be pre-labeled with their study ID, protecting each participant's PHI. No collections will take place in-clinic. These materials include all surveys, patient's diary, and all swab vials.

All vaginal swabs must be frozen within 48 hours of collection. As such, the participants will be asked to send their samples within 24 hours in order to give adequate time for delivery to the storage facility and be asked to collect their specimens between Sunday and Thursday so samples can reach the facility during business hours. Freezing will occur at the research site. Each patient's study kit will include a prepaid shipping envelope, which the participant can use to mail or drive their specimen to the research team who will then place it in the freezer until it is ready for analysis.

The first phase of the study will include an assessment and classification of patients' vaginal microbiome prior to receipt of the intervention. To get the best representation of the participant's baseline microbiome, the participant will be asked to collect their baseline swab no sooner than 10 days after menses, as menses-induced changes in the microbiome have been shown to resolve after this time¹². For similar reasons, if participants are being treated with an acute course of antibiotics or antifungals at the time of recruitment, they will be asked to wait 10 days after the completion of their medication course before collecting their baseline swab. There will be two additional time points for collection: collection 2) at the end of the 30 day intervention, and collection 3) 30 days after completion of the intervention.

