The intervention will take place on a rolling basis, as patient participation will have no bearing on other participants. The intervention itself will take place over thirty days. 8 pre-filled vaginal inserters with vaginal gel, will be provided to each of the participants with verbal and written instructions for application. Patients will be instructed to use Phexxi twice per week, on the same days every week. Throughout the 30 days, participants will also be asked to keep a diary of events (Appendix E) occurring when they used the product, such as intercourse or menses, as well as record any symptoms or side effects they noticed when using the product. The diary can be sent back with the second specimen vial. Disposal of the product may be done in a regular waste basket.

Approximately 30 days after completion of the intervention, participants will receive an email reminder to collect and send a third collection swab in (Appendix G) for analysis. This email will also include the link for the third and final set of surveys (B and C).

2. Data analysis and monitoring (include adverse event reporting procedures)

The pre-and post-intervention results will be compared with the subjects to serve as their own controls in this pilot study. To assess for the primary outcomes, each bacteria identified in the NextGen analyses of the composition of the pre-intervention microbiome sampling will be individually named, then classified as either “lactic acid-forming (LAF)” or “not lactic acid-forming (NLF)”. This will allow us to identify which CST each participant falls under prior to the study, and to assess if they can be classified under a different CST at the end of the study. It also allows us to conduct an independent t-test to test for significance between two variables (LAF/NLF) pre and post-intervention.

Demographic data will be collected from patient surveys. Demographic information to be collected will include age, ethnicity, number of reported vaginal yeast infections or BV infections in the last year, type of contraception used, type of diet, and medical comorbidities/current medications. This demographic information will allow us to perform a multiple regression analysis on our data set to account for confounding factors in our study population.

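### The Appendix E diary form dates the second specimen 30 days after the end of treatment, which is when the protocol body schedules the third and last swab

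*Protocol*

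**What the plan says.** Section III.1 (Study design and methods) plans a baseline swab and two later ones: "collection 2) at the end of the 30 day intervention, and collection 3) 30 days after completion of the intervention". The symptom survey (Survey B) follows the same pattern and "will be administered prior to, immediately after, and 30 days after intervention". On the diary, the section says "The diary can be sent back with the second specimen vial". For the final swab it says "Approximately 30 days after completion of the intervention, participants will receive an email reminder to collect and send a third collection swab". The email itself (Appendix G) asks for the last swab at about that time.

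Collection is unsupervised: "Samples will be self-collected by participants at their home at intervals specified in the study instructions".

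The diary form that the participant holds (Appendix E) ends with this line: "Please return this diary with your second collection specimen, 30 days after you have completed the study drug".

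**The concern.** Appendix E and Section III.1 agree that the diary travels with the second specimen. They disagree on when that specimen is due. Section III.1 puts it at the end of the intervention, and Appendix E puts it 30 days after the drug is finished, which is the date of the third swab.

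The line matters because participants act on the form at home, with no clinic visit at which a missed swab would be noticed. The end-of-treatment sample is where a direct effect of the gel on the microbiome would be seen. It cannot be collected afterwards.

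The surveys could move as well. Survey B belongs to all three collection points and Survey C to the second and third. Survey B asks about the past week (Appendix C). If a woman completes it with a late second swab, her symptoms at the end of treatment are not recorded. Microbiome change and symptoms are both primary outcomes. The diary, which records side effects during use, would also come back about a month late.

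**Working it through.** The protocol states no figure to reproduce here. The check sets the texts side by side and counts days.

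**What each place says**

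| Place | Second specimen | Third specimen |
|---|---|---|
| Section III.1, collection schedule | end of the 30-day intervention | 30 days after completion |
| Section III.1, Survey B times | immediately after | 30 days after |
| Section III.1, reminder procedure | no date given | about 30 days after completion |
| Appendix G | not mentioned | about 30 days after the course (the last swab) |
| Appendix E | 30 days after completing the drug | not mentioned |

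Appendix E is the only entry out of line. Reading its date as applying to the return of the diary does not help, because the diary is to go back with the second specimen. That specimen is still dated about a month late.

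**Day counts, with day 1 = first application**

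- Inputs from Section III.1: a 30-day intervention, "8 pre-filled vaginal inserters with vaginal gel, will be provided to each of the participants", and "Patients will be instructed to use Phexxi twice per week, on the same days every week". Eight applications at two per week take 4 weeks.
- Let k be the number of days from the first to the second application, from 1 to 6. The eighth application falls three weeks after the second: day 1 + k + 21. That is day 23 (k = 1) to day 28 (k = 6).
- Section III.1: swab 2 at about day 30, swab 3 at about day 30 + 30 = 60.
- Appendix E, counted from the last application: day 23 + 30 = 53 to day 28 + 30 = 58.
- Appendix E, counted from the end of the 30-day intervention: day 30 + 30 = 60.
- Delay of swab 2: from 53 − 30 = 23 days to 60 − 30 = 30 days.

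The swab that the form calls the second thus falls on the date of the third or within about a week before it.

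**What else could prompt swab 2 on time**

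- Appendix A, the swab instructions shown, covers technique and gives no dates.
- The one email reminder described is for swab 3.
- The two payments (Section V.8) follow the baseline sample and the third collection.

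**Weight of one loss**

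Section II.1 aims for 20 women after drop-outs. Each missing end-of-treatment swab removes 1/20 = 5% of the baseline to end-of-treatment pairs.

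**The case against.** The strongest reply is that this is a slip in one footer line, probably meant as 30 days after starting, and that the design itself is stated clearly and consistently in Section III.1. The line is mainly about returning the diary. Swab dates belong to the study instructions in the kit, which are not shown and may well be right. A woman might take her swab on time and be unsure only about when to post the diary. Surveys B and C at the second collection point also give some cue that a task is due at the end of treatment. Finally, the 23-day end of the range comes from using a different starting point for Appendix E than for the body. Measured from the end of the intervention in both, the gap is simply 30 days.

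Much of this stands. The design is not in question, a slip is the likely origin, and the number of women who would be misled is unknown. The choice of starting point affects only the size of the delay, not the conflict.

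It does not remove the point. The form says completed, not started. Among the participant materials shown, it is the only one that dates the second swab. The surveys are not shown to be a dated prompt, and Section III.1 lists them among the materials in the same take-home kit. The reminder's mention of a last swab could reveal a missed one, but only after the time point has passed.

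**Conclusion.** The contradiction is real and no reading of the text removes it. Appendix E gives the second specimen the date of the third. A woman who follows the form as written takes her second swab 23 to 30 days late, depending on whether she counts from her last application or from the end of the 30-day period. She then contributes two of the three planned time points.

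The loss is confined to the end-of-treatment sample, with the surveys if they are completed alongside it. Baseline and follow-up swabs remain, so the pre-post comparison survives in part. The size of the delay assumes eight applications on the same two days each week and collection on the stated dates. The limit to Sunday-to-Thursday collection would move actual dates by a few days. No effect on power is claimed, because the number of women affected cannot be derived from the protocol.

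This should be corrected before the form is used. It is not fatal to the design.

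**What to change.** Change the closing line of Appendix E to match Section III.1: the diary goes back with the second specimen, which is collected at the end of the intervention. Then check that the timing instructions in the take-home kit give the same date for swab 2 and keep the date 30 days after completion for swab 3.

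The cost is one corrected line in a participant form and a read-through of the kit instructions. Design, sample size and budget are unchanged.
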